9.2.10 Sample SAS code for the subgroup analysis with baseline GCA classification factor

```
ods output estimates=est Tests3=FixF;  
ods graphics on;  
proc mixed data=adef_subgroup covtest;  
  class Trt VisitWk GCAclass Agegroup Genotype usubjid;  
  model GCAchgBL = Agegroup Trt VisitWk Trt*Visitwk Trt* Agegroup GCABL Genotype/  
  ddfm=KR residual;  
  repeated VisitWk / type=un subject=usubjid rcorr;
```

```
estimate "Trt diff at Week 16" Trt 1 -1 Trt*VisitWk 1 0 0 0 -1 0 0 0 / cl;  
estimate "Trt diff at Week 28" Trt 1 -1 Trt*VisitWk 0 1 0 0 0 -1 0 0 / cl;  
estimate "Trt diff at Week 40" Trt 1 -1 Trt*VisitWk 0 0 1 0 0 0 -1 0 / cl;  
estimate "Trt diff at Week 52" Trt 1 -1 Trt*VisitWk 0 0 0 1 0 0 0 -1 / cl;  
lsmeans Trt*VisitWk / cl;  
run;
```

9.2.11 Sample SAS code for subgroup analysis testing treatment interaction

```
ods output estimates=est Tests3=FixF;  
ods graphics on;  
proc mixed data=adefc covtest;  
  class Trt VisitWk GCAclass Agegroup Genotype usubjid;  
  model GCAchgBL = Trt VisitWk GCABL Trt*Visitwk Trt* GCABL Trt*Visitwk*GCABL  
  GCAclass Agegroup Genotype/ ddfm=kr solution;  
  repeated VisitWk / type=un subject=usubjid rcorr;  
  estimate "Trt diff at Week 16" GCABL 25th_of_BL_GCA_distribution Trt 1 -1 Trt*VisitWk  
  1 0 0 0 -1 0 0 0 / cl;  
  estimate "Trt diff at Week 28" GCABL 25th_of_BL_GCA_distribution Trt 1 -1 Trt*VisitWk  
  0 1 0 0 0 -1 0 0 / cl;  
  estimate "Trt diff at Week 40" GCABL 25th_of_BL_GCA_distribution Trt 1 -1 Trt*VisitWk  
  0 0 1 0 0 0 -1 0 / cl;  
  estimate "Trt diff at Week 52" GCABL 25th_of_BL_GCA_distribution Trt 1 -1 Trt*VisitWk  
  0 0 0 1 0 0 0 -1 / cl;  
  estimate "Trt diff at Week 16" GCABL 50th_of_BL_GCA_distribution Trt 1 -1 Trt*VisitWk  
  1 0 0 0 -1 0 0 0 / cl;  
  estimate "Trt diff at Week 28" GCABL 50th_of_BL_GCA_distribution Trt 1 -1 Trt*VisitWk  
  0 1 0 0 0 -1 0 0 / cl;  
  estimate "Trt diff at Week 40" GCABL 50th_of_BL_GCA_distribution Trt 1 -1 Trt*VisitWk  
  0 0 1 0 0 0 -1 0 / cl;  
  estimate "Trt diff at Week 52" GCABL 50th_of_BL_GCA_distribution Trt 1 -1 Trt*VisitWk  
  0 0 0 1 0 0 0 -1 / cl;  
  estimate "Trt diff at Week 16" GCABL 75th_of_BL_GCA_distribution Trt 1 -1 Trt*VisitWk  
  1 0 0 0 -1 0 0 0 / cl;  
  estimate "Trt diff at Week 28" GCABL 75th_of_BL_GCA_distribution Trt 1 -1 Trt*VisitWk  
  0 1 0 0 0 -1 0 0 / cl;  
  estimate "Trt diff at Week 40" GCABL 75th_of_BL_GCA_distribution Trt 1 -1 Trt*VisitWk  
  0 0 1 0 0 0 -1 0 / cl;  
  estimate "Trt diff at Week 52" GCABL 75th_of_BL_GCA_distribution Trt 1 -1 Trt*VisitWk  
  0 0 0 1 0 0 0 -1 / cl;  
  lsmeans "Trt lsmeans at Q1" trt01pn*avisitn / at blgcass=Q1 / cl;  
  lsmeans "Trt lsmeans at Q2" trt01pn*avisitn / at blgcass=Q2 / cl;  
  lsmeans "Trt lsmeans at Q3" trt01pn*avisitn / at blgcass=Q3 / cl;  
run;  
Repeat for change from baseline in ABC score
```

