10.5.4 Exploratory Analyses

As exploratory analyses, the primary and key secondary MMRM models will be refit including the continuous baseline covariate by treatment interaction term in the model. Estimated least square means and 95% CIs for each treatment adjusting at the 25th, 50th, and 75th percentiles of the pooled baseline covariate distribution will be evaluated.

Additional subgroup analyses are planned for exploratory purposes for the change from baseline in GCA and ABC scores. An MMRM model will be used to test for subgroup interactions at the 10% significance level. In general, the model will include effects for treatment, visit week, treatment by visit week interaction, subgroup, treatment by subgroup interaction, subgroup by visit interaction and the 3-way interaction between treatment, visit and subgroup. The p-values from interaction tests will be presented, as well as the least square means and 95% CIs by treatment and visit within each subgroup. Descriptive statistics of observed values and change from baseline will also be presented by treatment and visit week within each subgroup.

A subgroup analysis will be performed for baseline GCA groups. For this analysis, patients with a baseline GCA score of greater than 70 will be classified as having “Moderate” cognitive impairment, while patients with a baseline GCA score equal to or below 70 will be classified as having “Severe” cognitive impairment. The randomization is stratified by this classification variable to ensure treatment group balance within these subgroups. Similar exploratory subgroup analyses may be performed for age group (either ≤ 6 years or > 6 years), language, geographic region or other baseline factors using MMRM.

A linear random coefficients model (ie, random slope and intercept for continuous time) will be fit for the primary and key secondary endpoints if appropriate. The average of the subject-specific slope estimates from the model will be compared between treatment groups using the two-sample t-test. To explore the relationship between composite scores and their components, correlations between the GCA and ABC scores (absolute value and change from baseline) and their respective domain scores will be estimated. Scatter plots will also be presented.

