The sample SAS code is presented in [appendix 9.2.9](#).

As exploratory analysis, the subgroup analysis will also be performed for the age subgroup with baseline age < 55 months and ≥ 55 months using an MMRM analysis in the same manner as described above for age subgroup with baseline age < 6 years.

The subgroup analyses will also be performed for the baseline GCA subgroup with baseline GCA score ≤ 70 and baseline GCA score > 70 . The change from baseline GCA score obtained at Visit Week 52 will be compared between the treatment groups using MMRM analysis. The repeated measures are the change from baseline GCA score obtained at the scheduled Visit Weeks 16, 28, 40, and 52, respectively. The model will include fixed categorical effects for treatment, visit week, treatment by visit week interaction, baseline age group (either <6 years or ≥ 6 years), treatment by baseline age group interaction, genotype and the baseline GCA score as a continuous covariate.

The sample SAS code is presented in [appendix 9.2.10](#).

The estimated least squares means and 95% confidence intervals on the treatment comparison at Visit Weeks 16, 28, 40, and 52 from MMRM model will be presented in Forest plots, including subgroup of baseline age < 6 years, baseline age < 55 months and baseline age ≥ 55 months, baseline GCA score ≤ 70 and baseline GCA score > 70 .

As exploratory analyses, the primary and key secondary MMRM models will be refit including the continuous baseline covariate by treatment interaction term and the 3-way interaction among treatment, visit week and the continuous baseline covariate in the model. The p value for the interaction terms and the estimated least squares means with their standard errors and 95% confidence intervals by treatment and visit at quartiles of GCA at baseline (25th, 50th and 75th percentiles) will be presented.

Due to small sample size of ITT Population with baseline age ≥ 6 years, MMRM model may fail to converge when low count of subjects with baseline age ≥ 6 years exists in either treatment group. If this model fails to converge, the treatment by baseline age group interaction will be removed from the model.

The sample SAS code is presented in [appendix 9.2.11](#).

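### The 12 treatment-difference ESTIMATE lines in SAP 9.2.11 put the baseline quartile on the wrong model term, so they do not estimate a treatment difference at that quartile

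*SAP*

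**What the plan says.** SAP 6.7.4 states that "the primary and key secondary MMRM models will be refit including the continuous baseline covariate by treatment interaction term", together with the three-way term in treatment, visit week and baseline. It asks for the interaction p-values and the "estimated least squares means with their standard errors and 95% confidence intervals by treatment and visit at quartiles of GCA at baseline". Protocol 10.5.4 describes the same kind of output, least squares means "for each treatment adjusting at the 25th, 50th, and 75th percentiles of the pooled baseline covariate distribution will be evaluated".

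SAP 6.7.4 points to SAP 9.2.11 for sample code. There the MODEL statement begins "model GCAchgBL = Trt VisitWk GCABL Trt*Visitwk Trt* GCABL Trt*Visitwk*GCABL", so the baseline slope may differ by arm and by visit. Twelve ESTIMATE lines follow, one for each of four visits at each of three quartiles, all labelled as treatment differences. Each has the form "GCABL 25th_of_BL_GCA_distribution Trt 1 -1 Trt*VisitWk" and then the eight visit coefficients. No line gives a coefficient for `Trt*GCABL` or `Trt*VisitWk*GCABL`. Three LSMEANS lines close the step, and the code is to be repeated for ABC.

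**The concern.** In a model whose baseline slope differs by arm, the treatment difference changes with baseline through the treatment-by-baseline terms. The baseline main effect is common to both arms and drops out of any difference. The ESTIMATE lines do the reverse: they load the quartile on the term that should be absent and leave out the terms that should carry it. If such a line returns a number, that number would be labelled a treatment difference at the quartile without being one. It would also change from quartile to quartile whenever the average baseline slope is not zero, even with no effect modification at all.

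**Working it through.** The plan states no figure for this analysis, so there is none to reproduce.

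**Inputs from the SAP.** The MODEL statement and ESTIMATE coefficients are in 9.2.11. The CLASS statement, "class Trt VisitWk GCAclass Agegroup Genotype usubjid", lists treatment before visit, so the eight `Trt*VisitWk` coefficients are in the right order. SAP 9.3.1 expects baseline GCA between 55 and 85.

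**Assumed inputs.** The documents give no quartiles or slopes. I assume quartiles q = 62, 70, 78, a true Week 52 difference of 11 at baseline 70, an average baseline slope s of -0.2, 0 or +0.2 per point, and an interaction slope d (difference in slope between arms at Week 52) of 0 or 0.2.

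**Target.** With arm-by-visit intercepts a and slopes b, the treatment difference at week w and baseline q is

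(a1w - a2w) + q(b1w - b2w).

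This needs coefficient 0 on `GCABL`, q and -q on `Trt*GCABL`, and q and -q on the two `Trt*VisitWk*GCABL` cells for week w.

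**Estimability of the coded line.** The `GCABL` column is the sum of the two `Trt*GCABL` columns and also the sum of the eight `Trt*VisitWk*GCABL` columns. An estimable function with q on `GCABL` must therefore have coefficients that sum to q within each of those two sets.

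- If the omitted terms are set to zero, the sums are 0 rather than q, and the line is non-estimable.
- If the coefficient is spread evenly (q/2 on each `Trt*GCABL` term, q/8 on each `Trt*VisitWk*GCABL` term), the line is estimable and equals (a1w - a2w) + q × (average slope over arms and visits). That is the arm difference at a baseline of 0, far outside 55 to 85, plus a slope term unrelated to treatment.

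**Numerical confirmation.** I built the design for 48 patients and four visits (35 columns, rank 22), with an assumed truth of 7.4, 11.0 and 14.6 at the three quartiles. The target vector returned 7.4, 11.0 and 14.6. The coded vector was non-estimable with zeros, and with spreading it returned -23.2, -23.6 and -23.9.

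**Size when the terms are spread.** A difference of 11 at baseline 70 makes the intercept difference 11 - 70d. Then:

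- correct value = 11 + d(q - 70)
- coded value = 11 - 70d + sq
- error = coded - correct = q(s - d)

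| s | d | Correct at 62/70/78 | Coded at 62/70/78 |
|---|---|---|---|
| 0 | 0 | 11/11/11 | 11/11/11 |
| +0.2 | 0.2 | 9.4/11/12.6 | 9.4/11.0/12.6 |
| +0.2 | 0 | 11/11/11 | 23.4/25.0/26.6 |
| -0.2 | 0 | 11/11/11 | -1.4/-3.0/-4.6 |
| 0 | 0.2 | 9.4/11/12.6 | -3.0/-3.0/-3.0 |
| -0.2 | 0.2 | 9.4/11/12.6 | -15.4/-17.0/-18.6 |

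For the last row at q = 62: 11 - 14 - 12.4 = -15.4, against 11 - 1.6 = 9.4.

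**The LSMEANS lines.** They have the right idea (evaluation at a baseline value), but they use `trt01pn`, `avisitn` and `blgcass`, none of which is in this CLASS or MODEL statement. They also carry a quoted label and a second slash. As typed they do not supply the planned least squares means.

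**The case against.** The strongest reply is that these lines are not the planned output. SAP 6.7.4 and protocol 10.5.4 ask for least squares means per treatment, not differences at quartiles. The interaction p-values come from the tests of fixed effects and do not depend on any ESTIMATE coefficient. SAP 9.2 calls this sample code and warns that names may change. All of that stands and limits the reach of the point. It does not remove it: the note on names does not cover wrong coefficients, the lines are labelled as treatment differences, and the LSMEANS lines that should give the planned output need repair as well.

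Three stronger readings are tempting, and the documents support none of them.

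- A reader might infer that the code would run cleanly and give wrong numbers without warning. The SAP does not say how unspecified terms are filled, and under one convention there is no estimate at all. The same step also has text placeholders for the percentiles and malformed LSMEANS lines, so it has to be edited before use.
- A reader might infer that this is the plan's only look at whether benefit depends on baseline cognition. SAP 6.7.4 also plans a treatment-by-GCA-class interaction model and separate models for baseline GCA of 70 or below and above 70. The separate-model code in 9.2.10 does not have this defect.
- A reader might infer that the sign of the benefit would be reversed. That depends on assumed slopes: the table runs from no error to a reversal.

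**Conclusion.** The point holds as a coding error in one exploratory analysis. As written, none of the 12 lines estimates a treatment difference at the stated baseline quartile under either convention for omitted terms. That conclusion follows from the MODEL and ESTIMATE statements and needs no assumed values.

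The size does rest on assumptions. Where a number is returned, the error is q(s - d). Over the assumed slopes it runs from 78 × (-0.4) = -31.2 points to 78 × 0.2 = +15.6 points, and it is zero when the average slope equals the interaction slope. The trial's own data would fix the value, and the documents give no basis for predicting it.

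The primary analysis, the key secondary test, the multiplicity plan and the interaction p-values are untouched. It is a worthwhile correction to the code and does not threaten the trial's main conclusions.

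**What to change.** Replace the 12 ESTIMATE lines and the three LSMEANS lines in SAP 9.2.11 with one statement per quartile, using the model's own names:

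`lsmeans Trt*VisitWk / at GCABL=<quartile> diff cl;`

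This gives the least squares means that SAP 6.7.4 asks for and correct differences. Of the pairwise differences produced, report the four that compare the arms within the same week.

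If ESTIMATE is kept, remove `GCABL` from each line and add `Trt*GCABL q -q`. Then put q and -q on `Trt*VisitWk*GCABL` only in the two cells for the week concerned, with zeros elsewhere. For Week 52 that is `Trt*VisitWk*GCABL 0 0 0 q 0 0 0 -q`.

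Make the same change in the ABC version. The cost is a few lines of appendix code; no data collection, sample size or test in the multiplicity plan changes.

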9.3 Appendix III - MMRM Simulation to Assess Analytical Methods

9.3.1 Introduction

The primary efficacy endpoint of study HGT-HIT-094 is the change from baseline in the Global Conceptual Ability (GCA) score at Visit Month 13 (Week 52), as obtained by DAS-II testing. Patients are assessed using the DAS-II at Baseline (Screening Visit), Month 4 (Week 16), Month 7 (Week 28), Month 10 (Week 40) and Month 13 (Week 52). A total of 42 patients are to be randomized using a 2:1 allocation ratio (28 active IT patients, 14 control patients) stratified by baseline GCA score (≤ 70 or > 70). It is expected that patients will have a GCA score of between 55 and 85 at baseline.

The proposed primary analysis of the primary endpoint will compare the treatment groups using a linear mixed model repeated measures (MMRM) analysis. The repeated measures are the change from baseline GCA scores obtained at the scheduled Visit Months 4, 7, 10 and 13, respectively. An alternative analytical approach is to use Analysis of Covariance at Month 13 with Last/Worst-Observation Carried-Forward to impute any missing data (ANCOVA-L/WOCF). This approach requires that, within a given patient, the last/worst (lowest) observed score prior to Month 13 be used for the imputation of their missing Month 13 value.

A series of data simulation studies were conducted to compare a linear mixed model repeated measures (MMRM) analysis with Analysis of Covariance using Last/Worst-Observation Carried-Forward (ANCOVA-L/WOCF). The methods and results from the simulation studies are described below.

9.3.2 Simulation Methods

The baseline GCA score was generated as a normal random variable with a mean of 70 and standard deviation of 15 in both arms. An accept-reject approach was used to restrict the range of values to 55 to 85 (about 2/3 of the sample met this criterion). The records were divided into sets of 42 patients representing a clinical trial and randomly assigned to active or control groups in a 2:1 ratio using a Bernoulli distribution with parameter, $p = 2/3$. In this manner, approximately 3600 replications of a clinical trial dataset, each with 42 patients, were simulated.

In each replication, multivariate normal (MVN) data was generated for the repeated measures on the change in GCA score using SAS Proc SIMNORM with the following assumptions. Based on our Phase I/II data in the target population of interest, and under the alternative hypothesis, we assumed a 1 unit decline per month in GCA score in the untreated control arm. As up to 2 months may elapse between the baseline assessment and the start of idursulfase-IT treatment, a mean decline of 2 points at Month 13 would be expected if IT treatment was effective in stabilizing the decline. Therefore, under the alternative hypothesis the change in GCA data were generated assuming the following row vectors of mean changes and variances for the change from baseline corresponding to Months 4, 7, 10 and 13 in the control and active IT arms respectively:

Control: $\mu_c = (-4, -7, -10, -13)$, $\sigma^2 = (3^2, 5^2, 8^2, 10^2)$

Active: $\mu_a = (-2, -2, -2, -2)$, $\sigma^2 = (3^2, 5^2, 8^2, 10^2)$

This leads to the following row vector of mean treatment differences for the change from baseline (i.e. $\mu_a - \mu_c$): $\delta_a = (2, 5, 8, 11)$. The expected standard error of the mean difference at Month 13 is therefore $10(\sqrt{1/14+1/28})=3.3$. Similarly, under the null hypothesis of no treatment difference, MVN outcomes were generated with mean treatment differences $\delta_0 = (0, 0, 0, 0)$ with the same variances.

For each simulation, the data were generated using a first order auto-regressive (AR(1)) covariance structure with ij^{th} matrix element $\sigma_i\sigma_j\rho^{|i-j|}$, where the correlation between adjacent time points was set to $\rho = 0.80$. The covariance and correlation matrix was thus specified as displayed in [Tables A1](#) and [A2](#) respectively.

Table A1: Theoretical AR(1) Covariance Matrix for Repeated Measures (in change from baseline)				
	Month 4	Month 7	Month 10	Month 13
Month 4	9.00	12.00	15.36	15.36
Month 7		25.00	32.00	32.00
Month 10			64.00	64.00
Month 13				100.00

Table A2: Theoretical AR(1) Correlation Matrix for Repeated Measures (in change from baseline)				
	Month 4	Month 7	Month 10	Month 13
Month 4	1.000	0.800	0.640	0.512
Month 7		1.000	0.800	0.640
Month 10			1.000	0.800
Month 13				1.000

The MMRM model included effects for treatment, month, treatment by month interaction and baseline GCA score as a continuous covariate. SAS Proc Mixed with restricted maximum likelihood estimation (REML) and an unstructured (UN) within-patient covariance structure was used. Note that a UN covariance structure was used in MMRM analyses even though an AR(1) structure was used to simulate the data, so as not to favor MMRM. The Kenward-Roger approximation was used to estimate denominator degrees of freedom. Similarly, the ANCOVA model for Month 13 contained effects for treatment and baseline GCA score as a continuous covariate. All scenarios were re-run adding a stratification factor for baseline GCA score (≤ 70 versus > 70) to each model. As the results for this set of simulations were nearly identical, results from the first set of simulations without the stratification factor are shown below. Power at Month 13, for the null and alternative hypothesis scenarios, was calculated for each analysis method using a 5% significance level.

9.3.3 Missing data

Monotone missing data with differential drop-out by treatment after month 4 was generated using a logistic regression model for the probability of drop-out. Simulations with data missing at random (MAR) and missing not at random (MNAR) were performed. Under MAR, conditional on the variables in the model, the missing data depends on the observed outcomes, however, under MNAR, missing data depends on both observed and unobserved outcomes. For MAR data, the probability of drop-out at a particular time point was dependent on treatment and the observed score at the previous visit. For MNAR scenarios, the probability of missing data also depended on the current visit score, which was unobserved in the subsequent analysis. In both cases, the logistic model was specified such that worse scores (greater declines) resulted in a higher probability of missing data. An overall drop-out rate of approximately 20% was assumed, with higher drop-out in the control versus the active arm (approximately 30% versus 15%) under the alternative hypothesis and equal drop-out under the null hypothesis. No imputation for missing data was employed for the MMRM analysis. LOCF was used to impute missing data for the ANCOVA analysis (ANCOVA-LOCF). Note that LOCF and WOCF are expected to be very similar methods in these simulations and the results should apply to both methods since a mean monotonic decline in the control arm and a constant value after Month 4 in the active arm was assumed under the alternative hypothesis. A mean monotonic decline in both arms is assumed under the null hypothesis.

9.3.4 Results

Data generated under the Alternative Hypothesis.

9.3.4.1 Complete Data

Complete MVN data were initially generated as described above. [Tables A3](#) and [A4](#) display the resulting covariance and correlation matrices respectively, which are very consistent with the values of the parameters specified above in [Tables A1](#) and [A2](#).

	Month 4	Month 7	Month 10	Month 13
Month 4	8.966	11.943	15.295	15.200
Month 7		24.915	31.887	31.699
Month 10			63.809	63.385
Month 13				99.114

	Month 4	Month 7	Month 10	Month 13
Month 4	1.000	0.799	0.639	0.510
Month 7		1.000	0.799	0.639
Month 10			1.000	0.799
Month 13				1.000

The MMRM and ANCOVA models were fit to the complete data. [Table A5](#) displays the average observed and least squares means and standard errors from MMRM and ANCOVA across the approximately 3600 simulated trials for the mean treatment differences at each month. MMRM returns the expected mean difference estimates (i.e. estimates of $\delta_a = (2, 5, 8, 11)$). Observed and MMRM estimated standard errors were also similar at each Month. Estimates were nearly identical for MMRM and ANCOVA at Month 13. Based on a 5% significance level, the power for the MMRM and ANCOVA tests at Month 13 were 89.0% and 88.4% respectively. Of note, the MMRM estimated unstructured covariance was very close to the true values and there were no issues of model non-convergence despite the relatively small sample size in each simulated trial.

Table A5: Observed and Estimated Mean Treatment Differences (in change from baseline): Complete Data			
MONTH	Observed Mean (SE)	MMRM LSMean (SE)	ANCOVA-LOCF LSMean (SE)
4	1.981 (1.004)	1.983 (1.013)	
7	4.998 (1.696)	5.000 (1.701)	
10	8.034 (2.734)	8.037 (2.739)	
13	11.011 (3.377)	11.013 (3.382)	11.016 (3.417)

